## 11.0 Interim Analyses, DSMB and iSRC

### 11.1 Interim Analyses

Three interim analysis were performed, 7 days after the second dose, 6 weeks after dose 2 and for the booster dose until day 208. The analyses will be based on a data snapshot. As this trial is of exploratory nature and no inferential statistics are planned, no adjustment for multiple testing will be done. Depending on the evolving state of the current pandemic and the public health need, an early analysis may be performed, and a study report based on interim data may be written to engage with collaborators and/or regulators.

### 11.2 Safety Monitoring Committees

If any SAE considered as related to the trial vaccine according to the Investigator occurs at any time during the trial, all vaccinations will be put on hold. The DSMB will perform a comprehensive review of all relevant safety and reactogenicity data before making a decision to stop, continue, or modify vaccination (including evaluating lower doses).

The DSMB may recommend additional measures including modification or halt of the trial.

Group 2 (subjects  $>60$  years, 6  $\mu$ g) will be initiated in 4 sentinel subjects. These subjects should be vaccinated at least 60 minutes apart. Safety and reactogenicity data reported during an observation period of at least 24 hours after vaccination will be collected and reviewed by an iSRC. In this review, the iSRC will review all available safety data, but focus specifically on Grade 3 adverse reactions (defined as solicited systemic, solicited local, or unsolicited Grade 3 AEs considered as related to the trial vaccine). Based on this review, the iSRC will decide on continuation of enrollment of subjects at this dose level. In a next step, 8 additional sentinel subjects will be enrolled. Safety and reactogenicity data reported during an observation period of at least 24 hours after vaccination will be collected and reviewed by the iSRC. In this review, the iSRC will review all available safety data, but focus specifically on Grade 3 adverse reactions. The same procedure will be followed for Group 4 (subjects  $>60$  years, 12  $\mu$ g) and the iSRC will decide on continuation of enrollment of subjects at this dose level after review of the first 12 sentinel subjects.

## 12.0 Statistical Methods

Due to the exploratory nature of this trial, only descriptive statistics will be used. No confirmatory statistical inference will be performed.

All data collected during this study will be displayed in data listings, unless otherwise specified. Data listings will be sorted by dose level and subject identifier. Screening failures will be excluded from all listings and tables if not otherwise stated. Listings will include all relevant assigned/derived variables.

Unless otherwise noted, categorical variables will be summarized using counts and percentages. Descriptive statistics (mean, median, standard deviation (SD), Q1, and Q3, minimum and maximum values) for continuous variable will be presented. Mean, median, Q1 and Q3 will be presented to 1 decimal more than original data. SD will be presented with 2 decimals more than original data. Minimum and maximum will match the decimal points in the original data. Maximum number of decimals will be 4, unless otherwise stated.

Expansion for subjects 18 to 60 years of age may start once the final dose for subjects in this age category has been selected based on the data from Trial CV-NCOV-001. Expansion for subjects >60 years of age may start once the final dose for these subjects has been selected based on data from this trial. Subjects enrolled in the expansion cohorts will be handled in the same manner as subjects in the first phase of the study.

The analysis will be presented in the following manner if not otherwise stated:

- Age; Overall age, age 18-60 and age >60 (61 years or older),
- Dose; any, dose 1, dose 2, booster doses at day 57 and day 180
- CVnCoV, active control (hepatitis A vaccine, or pneumococcal vaccine), and total.

Subjects in the expansion cohorts will be presented together with subjects from the initial phase of the trial.

All data summaries and tabulations will be prepared using SAS Version 9.4 or higher.

### 12.1 Subject Disposition

The number and percentage of subjects who completed the 2-dose vaccination regimen, the 2-dose vaccination regimen and booster at either day 57 or day 180, completed study, and reason for discontinuing further vaccination and study will be presented with a breakdown of the corresponding reasons for early termination and discontinuation.

The number and percentage of subjects included in each analysis set will be provided. Reasons for exclusion from each analysis set will not be tabulated, but will be listed. Subjects not fulfilling any inclusion/exclusion criteria will be listed only.

### 12.2 Important Protocol Deviations

Per PRA processes, protocol deviations data will be entered into PRA system of record (PSO). The trial team and the Sponsor will conduct on-going reviews of the deviation data from PSO and the resulting set of evaluable subjects throughout the trial, adjusting the deviation criteria as seems appropriate.

Protocol deviation data will be reviewed prior to each formal analysis (i.e. interim analyses of final analyses) and if applicable important deviations leading to elimination of subjects from analysis sets will be identified. If applicable detailed definitions will be provided in the final signed minutes of the data review meetings prior to each formal analysis and prior to database lock. Important subject-level protocol deviation will be summarized and listed.

## 12.3 Demographic and Baseline Characteristics

Demographic characteristics to be summarized based on the safety set will include gender, ethnicity, race, age at informed consent (years), age group (18 - 60 years, >60 years, 18-50 years, >50 years), baseline immune status measured retrospectively, height (cm), weight (kg), BMI (kg/m^2) and childbearing potential.

Subjects who are unblinded or censored due to requesting to be unblinded for receiving a licensed/authorized COVID-19 vaccine will be presented in a separate summary table.

## 12.4 Medical History

Medical history will be coded using the Medical Dictionary for Regulatory Activities (MedDRA) using version 24.0 or higher. Medical history will be listed only using the safety set.

## 12.5 Trial Vaccine Exposure

The administrations of CVnCoV or the active control will be listed. The number and percentage of subjects who received at least one vaccination and the individual vaccinations on day 1 (dose 1), 29 (dose 2), day 57 (booster dose) and day 180 (booster dose) including the reasons for not receiving a dose (where available) will be summarized using the safety set.

## 12.6 Prior and Concomitant Medications and Vaccinations

Prior and concomitant medication will be summarized with number and percentage according to WHODRUG (Version March 2020 Global B3 or higher), by Anatomical Therapeutic Chemical (ATC) using the safety set. ATC level 1 and preferred name will be displayed in the tables and listings. Concomitant vaccinations will be identified via ATC. Medications with ATC level 2 code J07 are considered to be vaccinations. Concomitant medications and concomitant vaccinations will be listed as well.

## 12.7 Adjudication of COVID-19 Cases

This data will be listed only.

## 12.8 Adverse Events

The primary, secondary and exploratory endpoints will be analyzed overall, as well as in subjects retrospectively SARS-CoV-2 seronegative at baseline, and in subjects retrospectively SARS-CoV-2 seropositive at baseline as per the definition given in section 10.6.3.

Unsolicited AEs, including SAEs, and AESIs and solicited AE integrated to or recorded on the CRF will be coded using MedDRA Version 24.0 or higher, by SOC and PT.

If not stated otherwise, all summaries of unsolicited AEs will also include relevant solicited AEs.

For outputs presenting occurrence of AEs for a defined period after a dose, the following distinctions are made if not otherwise stated; by any dose, dose 1, dose 2 and booster at day 57 and day 180. Any dose is defined as a subject who received at least one dose of either CVnCoV or active control.

In general, percentages will be based on the number of subjects in the respective analysis set. In summary tables for AEs after the second or booster vaccination, percentages will be based on the number of subjects in the respective analysis set who received the second, or booster vaccination as applicable.

The primary and secondary safety endpoints will be analyzed using the safety set.

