## 9.5 Population Sets

### 9.5.1 Safety Analysis Set

The safety set will consist of all subjects who received at least 1 dose of trial vaccine and for whom any post-vaccination safety data are available. All safety data will be analyzed using the safety set, if not otherwise stated.

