## 10.3 Missing Data

Analysis of vaccination data will be done on a valid case basis, i.e., for missing observations, no imputation for missing data, such as last observation carried forward, will be applied. For nCoV spike protein antibodies and Virus Neutralization, concentration values marked as below the cut point (CP) will be set to 0.5\*CP.

No imputation of missing values will be done for any analysis (except the imputation for missing partial dates of AEs and concomitant medication). Reasons for discontinuation from the trial or trial vaccination will be listed and summarized.

Currently no replacement of drop-out subjects is foreseen.

For unsolicited AEs, solicited AEs occurring after Day 8 and concomitant medications, some missing or partially missing variables will be imputed as follows:

For AE or concomitant medication start date:

- If start date year value is missing, the date uncertainty is too high to impute a rational date. Therefore, if year value is missing, the imputed AE start date is set to missing.
- If start date year value is before the vaccination start date year value, started before the vaccination. Therefore:
  - If month is missing, the imputed start date is set to the mid-year point (i.e., 01JULYYYY).
  - If month is not missing, the imputed start date is set to the mid-month point (i.e., 15MONYYYY).
- If start date year value is equal to the vaccination start date year value, the start date month needs to be compared against the vaccination start date month, to determine the imputation rule to apply. Therefore:
  - If month is missing, the imputed month and imputed day is the same as start of vaccination
  - If month is lower than vaccination start date month and start date day is missing, the imputed start date is set to the mid-month point (i.e. 15MONYYYY).
  - If month is equal to the vaccination start date and start date day is missing, the start day will be set to the start day of vaccination.
  - If month is greater than the vaccination start date month and start date day is missing, the imputed start date is set to the beginning of the month (i.e., 01MONYYYY).
- If start date year value is greater than the vaccination start date year value, started after vaccination. Therefore,
  - If month is missing, the imputed start date is set to the year start point (i.e., 01JANYYYY).

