### 10.5.2 Solicited AEs

Solicited local AEs (injection site pain, redness, swelling and itching) and solicited systemic AEs (chills, fever, nausea/vomiting, diarrhea, headache, fatigue, myalgia and arthralgia) will be collected on the day of vaccination and the following 7 days for dose 1, dose 2 and booster dose on a specific diary and after that together with all AEs occurring throughout the trial.

The severity and relatedness for each separate solicited AE should be assessed by the investigator and recorded on the AE form in the eCRF. The severity will be assessed for each day and the relatedness will be assessed overall.

The investigator's assessments on the CRF for severity assessment will be used.

Relatedness will be set to related for solicited local AEs on day 1 to 8 with a non-missing grade > 0 even if it was assessed as not related by the investigator.

For solicited systemic AEs the assessment of relatedness by the investigator will be used for all AEs on day 1 to 8 with a non-missing grade > 0.

Relatedness will be set to missing for all solicited AEs on day 1 to 8 with a missing grade or grade 0.

In case there are more than one solicited AE with the same relationship to study vaccine on a specific day with the same type of reaction (e.g. myalgia, injection site pain, nausea/vomiting) but recorded as different events, records will be collapsed for that specific diary day. Thereby, if there are overlapping events with the same relationship on a given diary day, they will be collapsed and reported with the highest severity grade on that day. Overlapping events with different relationship to study vaccine will not be collapsed.

Solicited events reported as “Nausea” and “Vomiting” are considered to be of the same reaction type “Nausea/Vomiting”.

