## 12.8.2 Analysis Solicited AEs

The following summaries of solicited AEs within 7 days after each trial vaccination and within 7 days after any trial vaccination will be provided:

- Summary of solicited AEs, local AEs and systemic AEs, overall and by maximum grade
  - will also be presented by sex (female/male) for any dose, dose 1, dose 2 and booster dose regardless of retrospective serology status at baseline.
- Occurrence of local AEs, overall and by maximum grade
- Occurrence of systemic AEs, overall and by maximum grade
- Occurrence of related systemic AEs, overall and by maximum grade (mild / moderate / severe)
- Duration (days) of solicited AEs, overall and for grade 3 events
- Duration (days) of local AEs, overall and for grade 3 events
- Duration (days) of systemic AEs, overall and for grade 3 events
- Duration (days) of related systemic AEs, overall and for grade 3 events
- Daily summary of local AEs (only for each dose)
- Daily summary of systemic AEs (only for each dose)
- Daily summary of related systemic AEs (only for each dose)
- Summary of time of onset (Day) for grade 3 solicited AEs, any solicited AEs, local, systemic AEs, and related systemic AEs
- Time of onset (Day) of local AEs
- Time of onset (Day) of systemic AEs
- Time of onset (Day) of related systemic AEs
- Number and percentage of subjects with solicited Grade 3 adverse reaction(s) or SAEs considered as related to the trial vaccine according to the Investigator with the 95% credibility interval based on the Beta (0.5, 0.5) prior distribution for each dose level and dose will be calculated and summarized.
- Individual solicited local and systemic adverse events will be displayed in by-subject figures
- Individual grade 3 solicited local and systemic adverse events will be presented in a figure.

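### Solicited-AE percentages have no solicited-data condition on their denominator (SAP 12.8), which conflicts with the valid-case rule in SAP 10.3

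*SAP*

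**What the plan says.** SAP 12.8 gives the general rule for AE percentages: "In general, percentages will be based on the number of subjects in the respective analysis set". The later doses have a narrower rule: "percentages will be based on the number of subjects in the respective analysis set who received the second, or booster vaccination as applicable". It names the set: "The primary and secondary safety endpoints will be analyzed using the safety set". SAP 9.5.1 defines that set as "all subjects who received at least 1 dose of trial vaccine and for whom any post-vaccination safety data are available".

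SAP 12.8.2 lists the solicited-AE tables ("The following summaries of solicited AEs within 7 days after each trial vaccination and within 7 days after any trial vaccination will be provided") and gives no denominator of its own. One item on that list is the percentage with a related solicited Grade 3 reaction or related serious AE (SAE), with a 95% credibility interval under a Beta(0.5, 0.5) prior. SAP 10.5.10 computes such estimates by dividing by the total number of subjects plus the prior parameters.

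SAP 10.3 points the other way: "Analysis of vaccination data will be done on a valid case basis, i.e., for missing observations, no imputation for missing data". Protocol 10.3.6 has the same rule. SAP 10.5.2 foresees missing grades ("Relatedness will be set to missing for all solicited AEs on day 1 to 8 with a missing grade or grade 0") but does not say whether the subject then stays in the denominator.

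**The concern.** Safety-set membership is decided once per subject, and any post-vaccination safety data suffice. Vital signs taken before discharge, which the protocol schedules after each vaccination (Table 1 footnotes), could be enough. A subject with a full dose-1 diary and no solicited data after dose 2 therefore stays in the dose-2 denominator and cannot enter the numerator. Under SAP 12.8 as written that subject is reaction-free. Under SAP 10.3 the subject would be left out. Two programmers following the same SAP could produce different primary tables.

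The frequency and intensity of solicited AEs are the first primary endpoints (protocol 4.2.1, SAP 9.4), and an acceptable Grade 3 reaction rate is part of the sizing rationale (SAP 8.5.1). Under the literal rule the error can only lower a reported rate. It may also differ between doses, age groups and arms, because the missing share may differ.

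**Working it through.** **1. The plan's own figure.** The documents give neither an expected solicited-AE rate nor a missing-diary rate, so the nearest stated figure is the 76% in SAP 8.5.1 (n = 200, true Grade 3 reaction rate 20%, true seroconversion rate 97.5%).

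- Reaction condition: P(rate ≤ 33%) ≥ 80% under a Beta(0.5, 1.5) prior. It is met with 60 or fewer events; probability 0.9997.
- Seroconversion condition: P(rate > 95%) ≥ 90% under a Beta(1.9, 0.1) prior. It is met with 194 or more seroconverters; probability 0.7641.
- Product, assuming independence: 0.9997 x 0.7641 = 0.764, which agrees with 76%.

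This calculation takes all 200 subjects as evaluable.

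**2. Shift in a reported rate.** Let p be the true rate, and m the share of the denominator with neither diary nor site-captured solicited data, unrelated to reactions. The literal rule reports p x (1 − m), so the shift is −p x m. The values of m and p are assumptions.

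| Assumed m | p = 30% reported as | Shift | p = 80% reported as | Shift |
|---|---|---|---|---|
| 0% | 30.0% | 0 | 80.0% | 0 |
| 2% | 29.4% | −0.6 | 78.4% | −1.6 |
| 5% | 28.5% | −1.5 | 76.0% | −4.0 |
| 10% | 27.0% | −3.0 | 72.0% | −8.0 |

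**3. Grade 3 credibility interval.** The estimate is (x + 0.5)/(N + 1) and the limits come from Beta(x + 0.5, N − x + 0.5). Take 200 dosed and a 30% rate among those with data.

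- m = 5% (190 with data, 57 events): 57.5/201 = 28.6% (22.6 to 35.0) on N = 200; 57.5/191 = 30.1% (23.8 to 36.8) on N = 190.
- m = 10% (180 with data, 54 events): 54.5/201 = 27.1% (21.2 to 33.5) on N = 200; 54.5/181 = 30.1% (23.7 to 37.0) on N = 180.

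The literal denominator moves the estimate down and also makes the interval narrower than the data support.

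**4. Weight of one missing subject** (group sizes from SAP Tables 1 and 2).

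- Group 1: 1/11 = 9.1%.
- Group 2: 1/12 = 8.3%.
- A booster subgroup of 30: 1/30 = 3.3%.
- Controls per age group (10 + 20 = 30): 1/30 = 3.3%.
- CVnCoV 12 µg per age group (90 + 200 = 290, phases presented together under SAP 12.0): 1/290 = 0.3%.

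**5. If missingness is related to reactions.** Let a be the rate among subjects with data and b the rate among those without. The true rate is a(1 − m) + bm. The literal rule reports a(1 − m), an error of −bm. A denominator restricted to subjects with data reports a, an error of (a − b)m. The literal rule is never too high. The restricted denominator is too high when b < a, and it is the less accurate of the two when b is below a/2.

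**The case against.** The strongest reply is that the SAP does not say a missing diary is coded as no reaction. The rule in 12.8 opens with a qualifier and covers all AEs, so the valid-case rule in 10.3 can be read as governing missing solicited assessments. This stands as far as it goes: a reader might infer that the published rates are certain to be biased downward, and the documents do not support that. What they contain is a stated denominator and a stated missing-data rule that disagree, with nothing to reconcile them. The SAP can be explicit when it chooses: 12.9.3 bases seroconversion rates on the number available at the time point.

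Second, a missing diary is not the same as missing solicited data. Subjects who enter nothing are prompted and then contacted (protocol 9.1.1), AEs are asked about at each visit (protocol 9.1.1.2), and the investigator's severity assessment on the case report form is the one used (SAP 10.5.2). This stands, and it is why m is defined above as having neither source. These steps reduce m but do not guarantee zero.

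Third, a reader might take the denominator to be every vaccinated subject. It is not: the safety set requires some post-vaccination safety data, and the dose 2 and booster tables use only recipients of that dose.

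Fourth, a reader might argue that above 1 − 0.33/0.35 = 5.7% missing, a true 35% rate would appear to meet the 33% limit. The documents do not support this. The limit belongs to a posterior-probability condition used for sizing; at n = 200 that condition needs 60 or fewer events, a 30% rate, not a point estimate below 33%. The planned analysis reports an interval and applies no threshold.

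Finally, restricting the denominator has its own assumption, as step 5 shows. This is a reason to display the number without data beside each rate.

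**Conclusion.** The point holds as an unreconciled conflict between SAP 12.8 and 10.3, in which the literal reading of 12.8 dilutes the primary reactogenicity rates and the Grade 3 credibility interval by about p x m. This size rests on missingness unrelated to reactions and on assumed values of m, since the documents give none. At a 30% rate the dilution is at most 1.5 points if m is 5% or less, and nothing if data are complete. In the pooled 12 µg groups an isolated missing subject hardly matters. In the 6 µg groups, the booster subgroups and the controls, one such subject is 3% to 9% of the denominator. Because the trial is descriptive, no test, error rate or decision threshold is affected; what is at stake is the accuracy and reproducibility of the reported rates.

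**What to change.** Add to SAP 12.8.2:

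- For all solicited-AE percentages, the denominator is the safety-set subjects who received that dose and have at least one non-missing solicited assessment, from diary or eCRF, on days 1 to 8 after it. For the any-vaccination tables, such an assessment after at least one dose is enough.
- The same denominator applies to the Beta(0.5, 0.5) credibility interval. That interval also counts related SAEs, so any subject with such an event is kept in even without solicited data.
- Daily tables use subjects with non-missing data on that day.
- Each table shows, by dose and group, the number of dosed subjects without solicited data.
- Any change from the denominators used in the three interim analyses (SAP 11.1) is noted.

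SAP 6.0 allows amendment before final database lock. The cost is a short SAP insertion and one extra flag per subject and dose. Reported rates will be slightly higher where data are missing. A limit remains: a subject with a partly completed diary is still counted on the available days, so a reaction on a blank day is missed.

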## 8.7 Blinding/Unblinding

The Sponsor and safety monitoring committees will be unblinded for data from the randomized groups, but will take appropriate measures to ensure subject blinding is kept at site level until database lock. Subjects may request to be unblinded in case they are eligible for an authorized/licensed SARS-CoV-2 vaccine.

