	Safety set. Applicable for subjects who received a booster dose at day 57 or day 180. Subjects unblinded and/or received an authorized/ licensed vaccine during the course of the trial will be censored at the day after unblinding or receipt of authorized/ licensed vaccine (whichever is earlier).

ENDPOINTS (subject level)	ESTIMANDS (population level)

 
The frequencies, intensities, and duration of solicited local AEs on the day of the booster administration and the following 7 days by group.
 
The frequencies, intensities, duration, and relationship to trial vaccination of solicited systemic AEs on the day of the booster administration and the following 7 days by group.
 
The occurrence, intensities and relationship to trial vaccination of unsolicited AEs on the day of the booster administration and the following 28 days by group.
 
	
The number and percentage of subjects by group reporting:
 
 
Each solicited local AE within 7 days after each trial booster vaccination by intensity and overall
 
Each solicited systemic AE within 7 days after each trial booster vaccination by intensity, by relationship to trial vaccine and overall.
 
At least 1 unsolicited AEs, at least 1 grade 3 unsolicited AEs and each unsolicited AEs by SOC/PT occurring within 28 days after each trial booster vaccination and overall by causal relationship to trial vaccine and overall
 
The mean duration in days by group with standard deviation of solicited AEs (within the solicited period, total duration).
 

Secondary Immunogenicity	

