## 10.8 Censoring Rules for Subjects Unblinded and/or Treated with Alternate Licensed/Authorized Vaccine

Since the efficacy results from Trial CV-NCOV-004 are available and all subjects in this trial are currently eligible to receive a licensed/authorized vaccine, all subjects in this trial will be unblinded following protocol version 3.0. Hence, all subjects will be unblinded prior end of the trial, and their data will be censored in all analyses. The below rules are still applicable as subjects could request unblinding or became eligible to receive a licensed/authorized vaccine prior to the protocol V3.0.

The following censoring rules will be applied to these subjects to avoid any study bias.

- Subjects who are unblinded will be censored for the safety endpoints at the first day after unblinding. Any related follow-up data that is collected from censoring time point forward will be included in the listings output.
- Subjects who are unblinded but decide not to receive the alternate licensed/authorized vaccine and to stay in the study will be analyzed for immunogenicity as planned.
- Subjects who are unblinded, but decide to receive the alternate licensed/authorized vaccine, will have their immunogenicity data censored at the first day after receiving the alternate licensed/authorized vaccine. However, any related follow-up data that is collected from this time point forward will be included in the listings output.
- Subjects who received an alternate licensed/authorized vaccine without or before being unblinded will be censored for safety and immunogenicity at the first day after receiving the alternate licensed/authorized vaccine. As described above, data collected from the censoring timepoint forward will be included in the listings output.

This is summarized in Table 7.

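### Booster (and dose-2) AE percentages keep in the denominator any subject already censored for safety when that dose was given, so a rate with counted events is diluted if such a subject exists

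*SAP*

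**What the plan says.** The denominator is set in SAP 12.8: for AEs after the second or booster dose, "percentages will be based on the number of subjects in the respective analysis set who received the second, or booster vaccination as applicable". The analysis set is the safety set, which SAP 9.5.1 defines as "all subjects who received at least 1 dose of trial vaccine and for whom any post-vaccination safety data are available". Nothing in that definition depends on censoring, so a subject censored later stays in the set.

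The numerator is governed by SAP 10.8: "Subjects who are unblinded will be censored for the safety endpoints at the first day after unblinding". SAP Table 7 applies this whether or not a licensed vaccine follows. Subjects who take a licensed vaccine without or before unblinding "will be censored for safety and immunogenicity at the first day after receiving the alternate licensed/authorized vaccine". For data after the cut, "Any related follow-up data that is collected from censoring time point forward will be included in the listings output". The estimand table in SAP 9.4 repeats the rule for booster safety. Its population is safety-set booster recipients, and they are censored rather than removed.

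SAP 8.7 gives the main route to early censoring: "Subjects may request to be unblinded in case they are eligible for an authorized/licensed SARS-CoV-2 vaccine". SAP 12.8.2 adds a table of solicited Grade 3 adverse reactions or related SAEs "with the 95% credibility interval based on the Beta (0.5, 0.5) prior distribution for each dose level and dose".

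**The concern.** The two parts of the fraction follow different rules. Events stop counting at the censoring date, but the denominator asks only whether the dose was given. A subject censored before a dose adds 1 to the denominator and can add nothing to the numerator.

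The figures at stake are the post-booster solicited-AE and Grade 3 percentages, which belong to the secondary safety endpoints, and the Beta(0.5,0.5) interval reported by dose. Once an event is counted, the error can go in one direction only, towards better apparent tolerability. The booster cells are small (30 planned in each), so a single subject has some weight.

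**Working it through.** The documents give no AE rate and no count of censored subjects for this point, so there is no stated figure to reproduce.

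**Can a censored subject receive a later dose?**
- SAP 10.8 foresees subjects who are unblinded, decline a licensed vaccine and stay in the study.
- Protocol 7.3.1 lets a subject continue after an emergency code break.
- Protocol 8.1 does not name unblinding as a reason to stop dosing.
- Protocol 7.7 allows licensed SARS-CoV-2 vaccines.

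So the documents do not bar it.

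**When is it plausible?** The 12 µg groups entered with protocol 2.0, dated 20 October 2020. Day 180 is 179 days after Day 1, so the earliest nominal 12 µg Day 180 visit is 17 April 2021, or 7 April 2021 with the 10-day early window. SAP 2.0, dated 1 April 2021, had already added the censoring rules. The sponsor was therefore planning for unblinding before any 12 µg Day 180 booster could be given. Dose 2 (Day 29) and the Day 57 booster have no comparable support.

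**Dilution formula.** Let N be the safety-set recipients of the dose, k the recipients already censored when it was given, x the recipients with a countable event, and p the event rate among the N - k subjects whose events can count.
- As specified: x/N, with expected value p × (N - k)/N.
- Among subjects whose events can count: x/(N - k), with expected value p.
- Relative loss: k/N.

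**Sizes of N** (protocol Table 2 and Table 5): 30 for each booster cell; 60 for the Day 180 booster over both age groups (30 + 30); 290 for dose 2 at 12 µg in one age group (90 + 200); 603 for all CVnCoV recipients. The loss per censored subject is 1/N: 3.3%, 1.7%, 0.34% and 0.17%.

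**Tabulated rate for assumed k** (20% is one of the adverse reaction rates in SAP Table 4; 80% is an assumed any-reaction rate):

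| k | N=30, p=20% | N=30, p=80% | N=60, p=20% |
|---|---|---|---|
| 0 | 20.0% | 80.0% | 20.0% |
| 1 | 19.3% | 77.3% | 19.7% |
| 2 | 18.7% | 74.7% | 19.3% |
| 3 | 18.0% | 72.0% | 19.0% |

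**Grade 3 interval.** By SAP 10.5.10 the posterior is Beta(x + 0.5, n - x + 0.5). With 6 countable reactors:
- As specified, 6/30 = 20.0% (95% credibility interval 8.8 to 36.7).
- Corrected for k=1, 6/29 = 20.7% (9.1 to 37.8).
- Corrected for k=3, 6/27 = 22.2% (9.8 to 40.2).

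For the two Day 180 cells together, 12/60 = 20.0% (11.4 to 31.4) compares with 12/57 = 21.1% (12.1 to 32.9) at k=3.

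**The case against.** The strongest objection is that the condition may never have occurred. It needs a subject who was censored first and dosed afterwards. Someone who asks to be unblinded in order to get a licensed vaccine has little reason to accept a CVnCoV booster, and exclusion criteria 2 and 3 (protocol 6.2) point the same way, although they apply at enrolment. Protocol 7.3.2 asks unblinded subjects to stay for safety follow-up and does not mention further doses. All of this stands. It narrows the route to requested unblinding without a licensed vaccine, and k may be 0. The dates show opportunity, not occurrence.

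A second objection is that SAP 10.8 opens by saying that unblinded subjects' data will be censored in every analysis, which a programmer could take to cover the later dosing record too. That would remove the subject from both parts of the fraction. The operative rules do not support this: they censor safety endpoints, and SAP 12.8 counts receipt of the dose.

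A third is that the effect is small beside the interval width, the trial is descriptive, later events are listed, and SAP 12.3 gives unblinded or censored subjects a separate table. This is fair and sets the severity. But SAP 12.3 does not say whether that table shows if censoring came before a given dose, and the percentage itself stays uncorrected. The SAP also makes this distinction elsewhere: in SAP 12.9.3 seroconversion rates use the number available at the time point rather than the set total.

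**Conclusion.** The mismatch is in the text, and its consequence is conditional. If k subjects were already censored when a dose was given, every tabulated rate with at least one counted event is understated by the factor (1 - k/N). At N=30 that is 3.3% relative per subject. For dose 2 it is negligible. Severity is minor.

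A reader might infer more than the documents support:
- **That the booster rates are in fact biased.** The documents do not give k.
- **That every per-dose AE table is affected.** With no counted events the rate is 0% on either denominator, as in many rows by SOC and PT.
- **That the general unblinding under protocol 3.0 makes the problem widespread.** That version is dated 3 December 2021, and nothing in the documents places a booster dose after it.

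The sizes assume that receiving the open-label booster is not itself unblinding under SAP 10.8, which the SAP does not say. They also assume the planned cell sizes. They leave out a related dilution: a subject censored inside the 7- or 28-day window, including one unblinded on the dosing day, is treated as event-free for the rest of that window.

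**What to change.** In SAP 12.8, and for the Beta(0.5,0.5) interval in 12.8.2:

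1. Base each per-dose percentage on subjects who received that dose and were not already censored for safety under SAP 10.8 when it was given.
2. State in SAP 10.8 that receiving the open-label booster is not itself unblinding.
3. Under each table, footnote the number excluded by rule 1 and the number censored inside the 7- or 28-day window. The second group stays in the denominator and still dilutes the rate, so the reader needs its size.

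The cost is one denominator rule, one clarifying sentence and a footnote per table. The unblinding, licensed-vaccine and dosing dates are already needed to apply SAP 10.8, so no new data and no protocol change are required. SAP 6.0 allows an amended SAP before final database lock, so the rule can still govern the final analysis. If k is 0, the footnote will show it.
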